2.3 Suggested Perioperative Pro Forma

1. **Starvation / Nil by mouth status:** as per current anaesthetic department guidelines; 6 hours for solid food, 4 hours for free oral fluids, and 2 hours for clear oral fluids.
2. **Premedication:** Paracetamol 1 gram or 20mg/kg in patients less than 50kg.
3. **Primary anaesthetic technique:** spinal anaesthesia with either isobaric or heavy bupivacaine 0.5% to a maximum of 3ml (15mg). No additives (e.g. intrathecal morphine or fentanyl) are permitted.
4. **Sedation:** Midazolam 1-2mg may be used to help facilitate spinal anaesthetic placement. During surgery, Propofol either by constant infusion or target controlled infusion (TCI) may be used for patient satisfaction and safety.
5. **General Anaesthesia:** While it is suggested that general anaesthesia is avoided, this may be required in the event of the crisis or at the request of the patient and/or

the anaesthetist. If general anaesthesia is to be used, we suggest Propofol TCI as the primary agent.

6. **Rescue analgesia**: fentanyl boluses of 25-50mcg every 5 minutes can be used in conjunction with the sedation technique described above in the event of patient discomfort. This should be recorded on the patient chart and the reason for the administration noted on the study case reporting form (CRF).
7. **Local Infiltrative analgesia (LIA)**: Ropivacaine 0.2% (2mg/ml) 150mls (total 300mg) with adrenaline 5mcg/ml (total 750mcg) should be injected prior to implantation of the prostheses. The technique of injection should be methodical and follow the current standard of practice at Counties Manukau Health.
8. **Supplementary agents**: in patients where nonsteroidal anti-inflammatory drug (NSAID) use is not contraindicated, parecoxib 40mg should be given intraoperatively. This should be followed by celecoxib 100mg BD for the duration of hospitalization.
9. **Antiemetic Therapy**: Dexamethasone (4-8mg) and Ondansetron (4mg) should be administered as antiemetic therapy if not contraindicated.
10. **Intravenous fluid therapy**: at the discretion of the treating anaesthetist. In routine patients without haemorrhage, 1000-2000ml of balanced crystalloid solution is suggested.

In addition to these guidelines, the use of indwelling bladder catheter and tranexamic acid use is at the discretion of the treating surgeon and anaesthetist. Patient mobilisation should take place on the day of surgery and will be assisted by the ward based nursing and allied health staff.

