1.2 Background

Total knee arthroplasty (TKA) is offered to patients with significant disorders of the knee arising from ageing, degenerative disease or after trauma. With the ageing population, this procedure will become more frequent and consume increasing amounts of health care resources (1). Current guidelines for TKA patients place an emphasis on early mobilisation and discharge to back to the community for home-based rehabilitation (2).

Despite the potential for considerable functional improvement after surgery, TKA is a painful procedure (4). The perioperative analgesic management is one area in which the anaesthetist can influence patient satisfaction and early joint function. To facilitate early mobilisation and rapid discharge, there has been a shift away from traditional techniques that produce systemic side effects or motor weakness - both which hamper post-operative rehabilitation efforts (2,5).

At Counties Manukau Health, the use of high-volume infiltration of low concentration local anaesthesia (LIA) has become the cornerstone of pain management following TKA. This technique is supplemented with multimodal oral analgesia and/or peripheral nerve catheters. A recent study conducted at Counties Manukau confirmed the relative safety of LIA with no observations of toxicity after recording peak local anaesthesia levels between six and twenty-four hours after surgery indicating that there is capacity for additional local anaesthetic use in the perioperative period (6).

As the levels of local anaesthetic begin to fall, evidence from randomized controlled trials and metaanalyses suggest analgesic efficacy of LIA begins to wane (7). To prolong the duration of effective non-opioid analgesia, the anaesthetist can place a

peripheral nerve catheter under ultrasound guidance near the nerves supplying sensation to the operative knee. One such example is the adductor canal catheter (ACC) which provides ongoing pain relief by using local anaesthesia to dampen pain signals generated from the operative site (8,9). The ACC prolongs analgesia without significant motor blockade; patients are less reliant on opioid analgesia and are able to participate in rehabilitation. Evidence from randomised controlled trials suggests that the ACC is a safe intervention which is complementary, and may enhance, the effect of LIA (10).

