2.2 Exclusion criteria

- Refusal or inability to consent.
- Analgesic technique involving epidural or peripheral nerve blockade (single shot or continuous techniques)
- Nerve catheter placed outside accepted range (distal to femoral triangle down to the adductor canal)
- Allergies to medication used in the study or its constituents
- Significant kidney and liver dysfunction (CrCl < 30mls/min, AST/ALT >2x upper limit of normal)

- Surgical procedure performed outside of Counties Manukau Health facilities.
- Failure to site adductor canal catheter in the appropriate location.
- Patients on >30mg/day of oral morphine equivalent for any reason.
- Patients outside the specified age range of 18-80 years.
- Patients at extremes of weight e.g.<50kg or >150kg
- If surgical team do not wish to take part or give individually tailored treatment that violate study protocol.

The Anaesthetic and Surgical management of patients enrolled in this study is largely at the discretion of the treating specialists after discussion with the patient. An anaesthetic pro forma is suggested below – data surrounding deviation from this pro forma will be collected and included in the final analysis.

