2.4 Placement of the Adductor Canal Catheter

At the end of surgery after sterile surgical dressing have been applied, an ultrasound guided adductor canal catheter will be placed on the operative limb using an aseptic technique. A multiorifice catheter (e.g. Contiplex or Contiplex C *B.Braun AG, Melsungun, Germany*) should be placed either within the distal femoral triangle or within the adductor canal deep to the Sartorius muscle. At least 2cm catheter should be left beyond the end of the needle. The catheter can be secured with both tissue glue and/or a catheter anchoring device prior to the administration of a sterile dressing.

No local anaesthetic will be administered down the catheter until the attachment of the prescribed infusion in the post-anaesthesia care unit (PACU). Randomisation will have taken place using opaque envelopes. Both the participants and the research nurses will not be aware which treatment a particular patient is receiving whereas the PACU nurses involved in the programming of the infusion pump and attaching the infusion to the patient will not be blinded. Participants will be randomised to receive either:

1. Continuous infusion group – 5 mls/hr of ropivacaine 0.2% for 48 hours
2. Programmed intermittent bolus group – 10mls ropivacaine 0.2% every two hours for 48 hours.

The time of infusion commencement will be noted down and the trial will run for 48 hours from this point. During this trial period, the assessments will take place at specified time points; 24 hours, 48 hours and 72 hours after the commencement of the infusion.

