2.5 Trial Assessments

Primary outcome:

Total opioid consumption over 48 hours. This will be converted to oral morphine equivalents as per the methods prescribed by the Faculty of Pain Medicine of the Australian and New Zealand College of Anaesthetists.

(<http://fpm.anzca.edu.au/documents/opioid-dose-equivalence.pdf>)

Secondary outcomes:

- Quality of Recovery (QoR-15) scores collected 24 and 48 hours after commencement of the study infusion.
- Time to first assisted mobilisation measured in minutes after discharge from PACU.
- Passive range-of-movement on day 1 and day 2, 24 and 48 hours after commencing the study infusion.
- Number of doses of antiemetic required over the 48-hour study period.
- Hospital length of stay measured in days.
- Side effects including nausea and vomiting, pruritis and sedation (Pasero opioid-induced sedation scale) collected daily.
- “Timed up and go” or TUG test 24, 48 and 72 hours after commencement of study infusion; TUG test is the time in seconds it takes the patient to stand from the chair, walk 3 meters, turn around and sit down again.
- Passive range-of-motion; the range of knee flexion will be recorded by the research nurse using a goniometer at the same follow up time intervals.

Post-operative Analgesia:

- Regular paracetamol (1gram Q6h) and celecoxib (100mg BD) unless contraindications exist.
- Do not prescribe sustained release opioid preparations (OxyContin or M-Eslon)
- Avoid prescribing IV Morphine and Patient Controlled IV Analgesia, unless strong reasons exist (e.g. Chronic pain states or pre-existing therapy).
- Patient will have access to the following PRN analgesia if required.

- Sevredol: Morphine immediate release 10-20mg PO Q2 hours PRN
- Tramadol 50-100mg either PO or IV Q6 hours PRN
- Oxycodone Immediate release (OxyNorm): 5-10mg PO Q2 hours PRN

A trial safety and data adjudication committee with three members independent from the study will be established to adjudicate serious adverse events and determine the need to stop the administration of trial drugs. Given the established safety of the medicine and technique, it is anticipated that this should be infrequent.

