2.6 Benefits to Participants

Potential benefits to participants include helping healthcare providers determine the most efficacious mode of local anaesthetic administration through an ACC. This may lead to changes in care pathways at Counties-Manukau Health and could have considerable benefits for future patients undergoing TKA. Depending on the individual's mindset, the participation in clinical research can lead to considerable satisfaction. As there is no control or placebo group, active therapeutic interventions will not be withheld, participants are not at risk of missing out on the therapeutic benefit of an ACC.

For both the District Health Board and the wider anaesthetic community, the results of this study could provide some clarification to changes which may be required in our pathways for patient care after TKA. Should benefits be seen in mobilisation, satisfaction or hospital length of stay, there are obvious economic effects including the reduction in overall healthcare costs and improved compliance with rehabilitation protocols.

3. Statistical Considerations

The statistical assessment of trial data will be devised and performed by a biostatistician. Patient demographic, surgical and anaesthetic factors will be recorded and tabulated. Demographic data will be presented as number (percentage) for discrete observation and mean (standard deviation) for continuous parameters.

For primary outcome (analgesic consumption in oral morphine equivalents) a test for differences in means / variances will be performed as guided by the data. Statistical test will be two-tailed with $p=0.05$ used as the threshold for statistical significance. Where possible, the clinical relevance of a statistical test will be provided in addition to the p-value. Similar testing strategies will be used for the secondary outcomes with differences in discrete observations (e.g. yes/no data) determined using the Fisher Exact test.

4. Data collection and retention

Data collection will be performed primarily by a research nurse specialist and/or investigator who will visit postoperatively to obtain the necessary parameters on paper form – this will be stored inside a secure cabinet in the department of anaesthesia and pain medicine. A Microsoft Excel spread sheet will be designed with various worksheets for data collection and analysis – this will be password protected and only accessed by approved investigators from within the Counties Manukau Health network.

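### Time to first assisted mobilisation is likely to depend partly on time of day and staffing, and section 3 states no adjustment for the infusion start time that 2.4 already records

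*Protocol*

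**What the plan says.** Section 2.5 defines the secondary outcome as "Time to first assisted mobilisation measured in minutes after discharge from PACU". It sets no criterion for when a patient counts as ready to mobilise.

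The closing paragraph of 2.3 says of both arms: "Patient mobilisation should take place on the day of surgery and will be assisted by the ward based nursing and allied health staff".

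Both arms are also to receive the same infiltration under 2.3: "Ropivacaine 0.2% (2mg/ml) 150mls (total 300mg) with adrenaline 5mcg/ml (total 750mcg) should be injected prior to implantation of the prostheses". Section 1.2 cites a local study "recording peak local anaesthesia levels between six and twenty-four hours after surgery" and says that the analgesic effect of infiltration wanes as levels fall.

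Catheter treatment begins in PACU. Section 2.4 says of its start: "The time of infusion commencement will be noted down".

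For the analysis, section 3 describes a two-tailed comparison of means or variances for the primary outcome and adds: "Similar testing strategies will be used for the secondary outcomes". It names no covariate for any outcome.

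**The concern.** The event that stops the clock needs staff at the bedside as well as a comfortable patient. It is aimed at the same day in both arms, at a time when a shared analgesic component is probably still working. If a late arrival on the ward is first mobilised the next morning, the hours of the night enter the outcome although they say nothing about how the ropivacaine was delivered.

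A plain two-group comparison leaves that variation in the error term. The risk is a wide confidence interval and a null result that says little about continuous infusion against programmed bolus. Section 2.6 names mobilisation among the possible benefits with economic consequences, so this outcome may well be cited when the trial is interpreted.

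**Working it through.** The protocol gives no effect size, standard deviation or power for this outcome, so there is no stated figure to reproduce. Three checks follow. The first uses protocol figures only; the other two rest on assumptions.

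**1. Catheter exposure on the day of surgery.** Ropivacaine 0.2% is 2 mg/ml. Continuous arm: 5 ml/h × 2 mg/ml = 10 mg/h. Bolus arm: 10 ml × 2 mg/ml = 20 mg every 2 h. The time of the first bolus (0 h or 2 h) is not stated, so the bolus arm is shown as a range.

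| Hours from start | Continuous | Bolus | Infiltration, both arms |
|---|---|---|---|
| 4 | 40 mg | 40-60 mg | 300 mg |
| 6 | 60 mg | 60-80 mg | 300 mg |
| 8 | 80 mg | 80-100 mg | 300 mg |

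At these times the arms differ by at most one 20 mg bolus, plus the mode of delivery. By the account in 1.2, a same-day mobilisation falls before or around the peak of the infiltration drug. It is therefore likely, though not shown, that the outcome is insensitive to delivery mode on that day.

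**2. Variance explained by start time.** All inputs here are assumptions.
- 60% early starts, mobilised at mean 300 min (SD 90).
- 40% late starts. A share *p* of these is mobilised next morning at mean 1000 min (SD 120), and the rest at 300 min (SD 90).
- 25 per arm, a total of 50, inside the 40 to 60 that 1.4 reports for similar trials.

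Between-class variance: B = 0.6 × 0.4 × (700*p*)².

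Within-class variance: W = 0.6 × 8,100 + 0.4 × [(1−*p*) × 8,100 + *p* × 14,400 + *p*(1−*p*) × 700²].

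R² = B/(B+W). The standard error (SE) of the difference in means is SD × √(2/25), with SD = √(B+W) unadjusted and √W adjusted.

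| *p* | B | W | R² | SD, min | SE, min |
|---|---|---|---|---|---|
| 0 | 0 | 8,100 | 0 | 90 → 90 | 25 → 25 |
| 0.5 | 29,400 | 58,360 | 0.335 | 296 → 242 | 84 → 68 |
| 1 | 117,600 | 10,620 | 0.917 | 358 → 103 | 101 → 29 |

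One patient moving from same day to next morning shifts a 25-patient arm mean by 700/25 = 28 min. The table treats start time as two classes. A straight-line term in clock time would recover less if the true relation is a step.

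**3. Power.** Take an effect that would have 80% power (two-sided α = 0.05) with no scheduling variance, and let *s* be the assumed share of total variance due to scheduling. The SD is inflated by 1/√(1−*s*), so power ≈ Φ((1.96 + 0.84) × √(1−*s*) − 1.96). This gives 68% at *s* = 0.25, 51% at 0.50, 29% at 0.75 and 14% at 0.90. The result is the same for 40 or 60 patients, because the effect is set relative to the sample size. The protocol has no data from which to choose *s*.

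**The case against.** Much of the opposing case stands, and it rules out several stronger readings.

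- **A reader might infer that the pathway fixes the outcome.** It does not. The same-day target is a recommendation in a suggested pro forma, and 2.2 says of that pro forma: "An anaesthetic pro forma is suggested below – data surrounding deviation from this pro forma will be collected and included in the final analysis". If the target did fix the day, there would be no overnight waits to worry about.
- **A reader might infer that the outcome mainly measures theatre-list position.** The protocol says nothing about list order, start times or allied health hours. Counting from PACU discharge removes the direct delay of a late operation. Ward nurses are named alongside allied health staff, so an evening mobilisation may well be possible. Only the indirect route through overnight waiting remains.
- **A reader might infer that the spinal is still acting at first mobilisation.** Section 2.3 caps its dose but gives no duration. Only the infiltration point has support in the text.
- **A reader might infer that exposure to the catheter technique is always brief.** A patient first mobilised at about 1000 min has had 1000/60 = 16.7 hours or more of treatment, about eight two-hourly boluses.
- **A reader might infer that chance imbalance in start times produces spurious differences.** Under 1:1 randomisation start time is balanced in expectation, and its variance is already in the unadjusted standard error. The false-positive rate stays near its nominal level.

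It is also fair to say that the variance figures follow from the assumed 700-minute gap, and that covariate adjustment is often left to an analysis plan, which is not shown here. Section 3 neither specifies nor excludes it. The point is therefore a better method for one outcome, not an error in the protocol. What the objections leave untouched is that the event is staff-dependent, has no readiness criterion, can include a night, and is paired with a plain two-group test although a useful covariate is already being collected.

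**Conclusion.** The concern holds as a minor point about precision and interpretability for one secondary outcome. The primary outcome, opioid use over 48 hours, is unaffected, and the timed up-and-go tests at 24, 48 and 72 hours measure function at later, set times.

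The size cannot be fixed from the protocol. Under the assumed 60/40 split and 700-minute gap, start time explains about 33% of the variance if half of late starts wait until morning and about 92% if all do. The share falls to zero as next-day mobilisation becomes rare. At the one-half setting, adjustment is worth about as much as 87,760/58,360 = 1.5 times the patients for this outcome. That the infiltration blunts a difference between arms on the day of surgery is a reasonable inference from 1.2, not something the protocol demonstrates.

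**What to change.** In section 3, state that time to first assisted mobilisation is compared between arms with adjustment for the clock time of infusion start, and fix the form of that term in advance (linear, or a split at a stated hour). The start is noted before any drug has gone down the catheter, so the treatment itself cannot have affected it. Report alongside it the proportion in each arm mobilised on the day of surgery, which stays interpretable if the minutes fall into two clusters.

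Optionally, add one case report form item for patients not mobilised that day, giving the reason: pain, weakness, nausea or staff availability. This would help a reader to interpret a null result.

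The cost is one degree of freedom, a sentence of analysis wording and, if wanted, one form item. The covariate is already collected, and nothing in patient care changes.

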2.4 Placement of the Adductor Canal Catheter

At the end of surgery after sterile surgical dressing have been applied, an ultrasound guided adductor canal catheter will be placed on the operative limb using an aseptic technique. A multiorifice catheter (e.g. Contiplex or Contiplex C *B.Braun AG, Melsungun, Germany*) should be placed either within the distal femoral triangle or within the adductor canal deep to the Sartorius muscle. At least 2cm catheter should be left beyond the end of the needle. The catheter can be secured with both tissue glue and/or a catheter anchoring device prior to the administration of a sterile dressing.

No local anaesthetic will be administered down the catheter until the attachment of the prescribed infusion in the post-anaesthesia care unit (PACU). Randomisation will have taken place using opaque envelopes. Both the participants and the research nurses will not be aware which treatment a particular patient is receiving whereas the PACU nurses involved in the programming of the infusion pump and attaching the infusion to the patient will not be blinded. Participants will be randomised to receive either:

1. Continuous infusion group – 5 mls/hr of ropivacaine 0.2% for 48 hours
2. Programmed intermittent bolus group – 10mls ropivacaine 0.2% every two hours for 48 hours.

The time of infusion commencement will be noted down and the trial will run for 48 hours from this point. During this trial period, the assessments will take place at specified time points; 24 hours, 48 hours and 72 hours after the commencement of the infusion.

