1.4 Number of Patients

The study size will depend on the power calculation. This information is yet to be collected. Similar trials testing for differences in effect between continuous and intermittent bolus techniques have enrolled between 40 to 60 patients. Once the clinically significant treatment effect has been determined, we will calculate the sample size using standard techniques with $\alpha = 0.05$ and $\beta = 0.2$

2. Research Methods

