2.1 Study Design

This is a prospective randomized controlled trial for patients undergoing an elective, unilateral primary total knee arthroplasty. We aim to randomly allocate participants to one of two groups in a 1:1 fashion. The first group will receive a continuous infusion of local anaesthetic whereas the second group will receive a programmed intermittent bolus. Besides from this difference, the participants will all receive routine care after their TKA; this is a positive-control study in which there will be no placebo group. Both the participants and the research nurse assessing patient outcomes will not be aware of group allocations.

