2.2 Inclusion Criteria

We aim to enrol patients undergoing primary TKA in our institution prior to the day of surgery in the preadmission clinic or on the day of surgery at the time of surgical and anaesthetic consent. Adequate time for patient questions and a plain language explanation sheet will be provided to aid patient consent. The study will be completed at Middlemore Hospital and Manukau Surgical Centre. Consultation with the Maori and Pacific representatives will be sought as per current HDEC standards.

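### Two hospitals with largely discretionary care, but no stratification by hospital in the allocation and no hospital term in the stated primary test: a modest, cheaply avoided loss of precision

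*Protocol*

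**What the plan says.** **Sites.** Protocol section 2.2 (Inclusion Criteria): "The study will be completed at Middlemore Hospital and Manukau Surgical Centre".

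**Allocation.** Section 2.1: "We aim to randomly allocate participants to one of two groups in a 1:1 fashion". Section 2.4 adds only: "Randomisation will have taken place using opaque envelopes". The protocol gives no strata, no blocks and no way of generating the sequence. It does not say whether each hospital has its own envelopes.

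**Care.** Section 2.2 (Exclusion criteria): "The Anaesthetic and Surgical management of patients enrolled in this study is largely at the discretion of the treating specialists". The perioperative pro forma in 2.3 is a suggestion. Departures from it are to be recorded and brought into the final analysis in a way not specified.

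**Primary outcome.** Section 2.5: opioid use over 48 hours in oral morphine equivalents. The listed postoperative opioids are as-needed drugs, each with a dose range.

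**Analysis.** Section 3: a test of means or variances chosen in the light of the data, two-sided at 0.05, with no hospital term. A biostatistician is to devise the details.

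**Size.** Section 1.4: "The study size will depend on the power calculation. This information is yet to be collected". For context: "Similar trials testing for differences in effect between continuous and intermittent bolus techniques have enrolled between 40 to 60 patients".

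**The concern.** Where treating teams have wide latitude and the outcome is how much as-needed opioid a patient receives, the hospital may plausibly predict the outcome. The same holds for time to first assisted mobilisation and length of stay, which depend partly on ward routines. Nothing in the described allocation keeps the arms balanced within each hospital, and nothing in the stated primary test removes a hospital difference. In a small trial, such a difference would add noise to the comparison of continuous infusion with intermittent bolus. It could also push one trial's estimate in either direction by chance.

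Timing matters. A hospital term can be added in an analysis plan written later. Stratification is part of the allocation and cannot be added once envelopes have been opened, so its place is Sections 2.1 and 2.4 of the protocol.

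**Working it through.** The protocol gives no sample size, effect size or SD, so it has no figure of its own to reproduce. The check asks how large the issue would be under stated assumptions.

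**Inputs from the protocol:** two hospitals, 1:1 allocation, two-sided alpha 0.05, power 0.80 (beta 0.2).

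**Assumptions:** N = 40 or 60 (the range for similar trials in 1.4); 50% or 70% of patients from one hospital; a hospital effect g of 0.25, 0.5 or 0.8 within-hospital SD. The protocol supplies no value for the last two.

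**Step 1: chance of imbalance.** With n = N/2 per arm and K patients from hospital A, the number X of these in one arm is hypergeometric (N, K, n). The difference in hospital share is D = (2X − K)/n, with Var(D) = (4/n²) × n(K/N)(1 − K/N)(N − n)/(N − 1). For N = 40 and K = 20, Var(X) = 20 × 0.5 × 0.5 × 20/39 = 2.564, so Var(D) = 4 × 2.564/400 = 0.0256 and SD(D) = 0.160. A gap of 20 points means X lies at least 2 from K/2 at N = 40, or at least 3 from it at N = 60.

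| N | Share from one hospital | SD(D) | P(gap ≥ 20 points) |
|---|---|---|---|
| 40 | 50% | 0.160 | 34% |
| 40 | 70% | 0.147 | 30% |
| 60 | 50% | 0.130 | 20% |
| 60 | 70% | 0.119 | 16% |

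**Step 2: shift in a single trial.** Shift = gap × g. With a 20-point gap and g = 0.5 SD, 0.20 × 0.5 = 0.10 SD. The effect detectable with 80% power is (1.960 + 0.842) × √(2/n): 0.89 SD at n = 20 and 0.72 SD at n = 30. The shift is therefore about 11% (0.10/0.886) to 14% (0.10/0.723) of that effect.

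**Step 3: validity and precision over repeated trials.** Simulation with 8,000 runs per setting and a 50/50 hospital split. For the unstratified, unadjusted t-test, type I error was 0.050 to 0.053 and mean bias about 0. Power at the detectable effect:

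| N | g (SD) | Unstratified, unadjusted | Unstratified, adjusted | Stratified and adjusted | Gain, last vs first (points) |
|---|---|---|---|---|---|
| 40 | 0.25 | 0.774 | 0.771 | 0.776 | 0.2 |
| 40 | 0.5 | 0.744 | 0.760 | 0.782 | 3.8 |
| 40 | 0.8 | 0.717 | 0.769 | 0.771 | 5.4 |
| 60 | 0.25 | 0.777 | 0.780 | 0.795 | 1.8 |
| 60 | 0.5 | 0.761 | 0.781 | 0.797 | 3.6 |
| 60 | 0.8 | 0.721 | 0.780 | 0.796 | 7.5 |

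The simulation error of each power figure is about √(0.78 × 0.22/8000) = 0.005, so differences of a point or so should not be over-read.

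**Step 4: cross-check by formula.** In SD units, the variance of the unadjusted difference is 2/n + g² × Var(D). For N = 40 and g = 0.8 it is 0.100 + 0.64 × 0.0256 = 0.116, an SE of 0.341 against √0.100 = 0.316 with balance. The simulated values were 0.339 to 0.344 and 0.314. In the normal approximation, power is Φ(0.886/0.341 − 1.960) = 0.74 against 0.80, a loss of about 6 points. The same calculation gives losses of about 2.5 points for g = 0.5 and 0.6 for g = 0.25. The order of magnitude agrees.

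**The case against.** The strongest reply is that much of this rests on what the protocol leaves unsaid.

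- **Shared envelopes.** A reader might infer that both hospitals draw from one unstratified set. Section 2.4 does not say so, and nothing rules out blocks or separate sets. What stands is that the protocol does not commit to them.
- **No correction.** A reader might infer that a hospital difference would go unadjusted. That is not established: Section 3 leaves the detail to a biostatistician, departures from the pro forma are to enter the analysis, and an analysis plan not shown here could include hospital. Adjustment alone recovers much of the power (0.76 to 0.77 at N = 40, 0.78 at N = 60). This answers much of the analysis half of the point, but not the allocation half.
- **Hospital differences.** None is documented. Both hospitals belong to one health board and share a suggested pro forma, a local infiltration standard and an as-needed drug list. Teams whose tailored treatment breaches the protocol are excluded. Nor does the protocol say who gives the as-needed doses, so different ward habits in giving them are a possibility only. This is fair, and it is why the hospital effect is shown as a range starting at a small value.
- **Size.** The 40 to 60 figure describes similar trials. With a larger sample, a 20-point gap becomes less likely.

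**Conclusion.** The point stands as a cheap improvement; no statement in the protocol is shown to be wrong. With two hospitals, discretionary care and an outcome driven mainly by as-needed opioid, leaving hospital out of both the described allocation and the stated test gives up some precision. For a trial sized like its predecessors, the loss is about 0 to 2 power points if the assumed hospital effect is 0.25 SD, about 4 if it is 0.5 SD, and about 5 to 8 if it is 0.8 SD. These figures depend on the assumed N, hospital shares and hospital effects.

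Two stronger readings are not supported. One is that chance imbalance biases the comparison or makes the test invalid. Randomisation keeps the estimate unbiased over repeated trials, and the two-sample standard error already contains the between-hospital variation, so type I error stays near 0.05. The other is that the shift can be stated in milligrams of morphine. The protocol gives no mean, SD or hospital contrast for opioid use, so SD units are as far as the documents go.

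**What to change.** Before the first patient is enrolled, replace the envelope sentence in Section 2.4 with text such as: *Allocation is stratified by hospital (Middlemore Hospital, Manukau Surgical Centre) in randomly permuted blocks of varying size. The list is computer-generated by someone not involved in recruitment or care. Each hospital holds its own set of sequentially numbered, sealed, opaque envelopes.* In Section 3, state that the primary comparison includes hospital as a factor.

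The cost is a second envelope set, slightly longer preparation, and one degree of freedom. Patient care does not change. If the hospitals prove to be alike, almost nothing is lost.
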